Harnessing the Power of Technology: MOMBA for Postpartum Smoking NCT02237898

09/07/2017

Overview: Through a pilot, randomized control trial tested the effectiveness of Momba Live Long (the Momba Live Long application and sensor) on 7-day point prevalence of smoking abstinence rates i) at the end of the trial and ii) at 3-month follow-up as determined by the Timeline Follow Back instrument and number of negative breath tests.

The randomized controlled trial of Momba Live Long utilized a control group which received financial incentives at an in-person office/clinic visit based on expired CO levels obtained through the piCO+TM CO sensor compared to the MoMba Livelong application. We used results from frequently administered assessment instruments over the course of an 3-month period and subsequent 6- and 12-month follow ups to assess outcomes and to examine the reliability and validity of assessment measures, and key methodological parameters, such as effect size, proportion of eligible and willing study participants, attrition rate, time necessary for data collection, and necessary skill sets for CMHAs. The RCT involved an intervention arm (10 women who receive Momba Live Long) and "control" arm (10 women who receive financial incentives delivered in-person in the office). Participants were randomized using a number generation mechanism provided to the CMHAs who are screening and enrolling women.

Intervention Group (Momba Live Long): The intervention group received a smartphone, data plan, Momba Live Long, including the Bluetooth enabled CO sensor, and training from a CMHA on its use. The intervention group did most of its CO tests remotely, outside of a baseline, 3-month end point assessment, and 6-month and 12-month follow-ups. However, participants also came n for the first 5 days of week 1 to be trained on how to use the Sensordrone and Momba Live Long app. As part of this training, we showed the intervention group participants a Demonstration Video and a Powerpoint Presentation about how to use the Momba Live Long Application. Intervention group participants came to the office for a visit in Week 4 and Week 8 to calibrate the Sensordrone and to submit a urine specimen.

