Control Group: Control group mothers received traditional, in-office contingency management to prevent smoking relapse. Financial incentives were delivered according to the same schedule at the same frequency as those delivered to mothers on Momba Live Long. The exception was that mothers in Momba Live Long will also receive payment for completing tasks that promote abstinence. Overall, the amount of Contingency Management incentives in the two groups were similar. Thus, we were not directly comparing the effectiveness of contingency management that has already been well established, but rather we assess the effectiveness of contingency management delivered over a smartphone application vs. traditional contingency management in an office setting. Women in each condition were provided with the Staying Smoke Free curriculum. Mothers in the control condition completed the same assessment battery and according to the same schedule as participants in the Momba Live Long application group and were compensated similarly. During the first 3 months, control group participants completed assessments with staff during office visits. In months 4-12, surveys were administered via Qualtrics links on personal smartphones, over the phone with research staff, or by mailing the surveys to and from participants' homes. Control group CM breath tests were conducted with the piCO+TM, considered as "traditional" Contingency Management. They also completed Sensordrone CO tests for comparison purposes with the Intervention Group. Control participants were also be compensated for attending each scheduled CO test office visit.

Participants: Women who were smoking in the second or third trimester of pregnancy, with no complicating general medical or psychiatric conditions (including other substance use disorder) were eligible. Women were not receiving other smoking cessation medication. Mothers were not eligible to participate if they were planning to move out of the New Haven area in the next 15 months after study enrollment, had medical complications that would interfere with testing the Sensordrone, or were actively suicidal, psychotic or unable to provide informed consent.

Screening and Enrollment: We used rolling enrollment (over a

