To quantitatively evaluate the *feasibility* and *acceptability* of Momba Live Long to postpartum women we will begin by calculating the number of women screened and eligible and enrolled. We will collect data on reasons women are not enrolled. We will consider a participation rate of $\geq 60\%$ for eligible women between screening and enrollment as supportive of feasibility. We will evaluate retention and set a threshold of 80% for the Momba Live Long group. Since feasibility also depends upon compliance to the challenges or office visits through which contingency management is delivered, we will use challenge completion and in-office visit attendance to assess compliance. Mixed-effects regression models will be conducted as outlined above for group comparisons. Because number of visits attended is a count variable, random effects regression with a negative binomial model will be used which is appropriate for count data.(45) Additional procedures to evaluate abstinence from smoking are described below.

Data Analysis for Pilot RCT: Descriptive statistics will summarize the data on all screened and randomized subjects. Baseline demographic and clinical characteristics for the randomized groups will be compared using chi-square tests for categorical variables and analysis of variance for continuous variables. All continuous variables will be examined for adherence to the normal distribution using normal probability plots and Kolmogorov-Smirnov tests. Dropouts and completers will also be compared on baseline characteristics using the same approach. Data analyses will be conducted using the intent-to-treat principle. We will use mixed-effects regression models to compare the two groups (Momba Live Long vs. in-office contingency management) using SAS PROC MIXED version 9.3. These models allow for different numbers of observations per subject, use all available data on each subject, and are unaffected by randomly missing data. They are flexible in modeling the correlation structure of the data. In each model, we will include fixed effects of time, group (Momba vs. in-office) and time by group, and random subject effects. If there are concerns of informative dropout and/or informative intermittent missing data, we will use pattern mixture models to perform sensitivity analyses to our main analyses.

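### The plan defines no measure of contingency-management compliance that works in both arms, so the planned between-arm comparison of visit counts is not interpretable

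*Combined protocol and SAP*

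**What the plan says.** The feasibility part of the Proposed Analytic Plan takes feasibility to depend on "compliance to the challenges or office visits through which contingency management is delivered" and states that "we will use challenge completion and in-office visit attendance to assess compliance". It continues: "Mixed-effects regression models will be conducted as outlined above for group comparisons". For attendance it gives the scale: "Because number of visits attended is a count variable, random effects regression with a negative binomial model will be used". The model terms are under Data Analysis for Pilot RCT: fixed effects of time, group and their interaction, with random subject effects. The plan does not define challenges, assign a measure to an arm, or give a scheduled-visit denominator or offset.

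The delivery sections describe two different channels.

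- **Control Group:** "Control group mothers received traditional, in-office contingency management to prevent smoking relapse". On incentives: "Financial incentives were delivered according to the same schedule at the same frequency as those delivered to mothers on Momba Live Long". The stated exception is that Momba mothers were also paid for tasks that support abstinence.
- **Intervention Group:** "The intervention group did most of its CO tests remotely". These women attended on five days in week 1 for training and then "came to the office for a visit in Week 4 and Week 8 to calibrate the Sensordrone" and give urine.
- **In office monitoring** names no arm. It requires women to attend for CO tests on both devices: five days in week 1, twice in week 2, at most twice weekly in weeks 3-8 and at most weekly in weeks 9-12. It ties incentives to the breath test.

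**The concern.** A between-arm comparison needs a dependent variable that means the same thing in both arms. Challenge completion seems to have no value for controls. Office attendance is the delivery of contingency management for controls. For Momba women, on the Intervention Group schedule, it is mainly training and device calibration. The only compliance variable for which the plan names a count model is therefore one whose meaning and scheduled total can both differ by arm.

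Feasibility is a stated goal of the analysis, and the pilot is meant to inform a larger trial. A group effect on visits attended could be reported as better or worse compliance with smartphone delivery when it shows only who was asked to come in, and for what.

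**Working it through.** **The plan's own figure.** There is none for compliance. The feasibility thresholds (60% participation, 80% retention) and the 90% power statement concern other quantities and do not bear on this point.

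**What each measure records**

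| | Momba | Control |
|---|---|---|
| Challenge completion | Probably the paid app tasks, perhaps also remote CO tests; undefined | None described |
| Office visits (Intervention Group and Control Group sections) | Training, calibration, urine | Contingency management itself |
| CO tests | Mostly remote | Office |

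No row gives a measure, as the plan defines it, that records contingency-management compliance in both columns.

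**Scheduled office visits over 12 weeks**

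- Controls, from In office monitoring: 5 + 2 + (2 × 6) + (1 × 4) = 23 at most. After week 1: 23 − 5 = 18.
- Momba, from Intervention Group: 5 + 1 + 1 = 7, or 8 with the 3-month assessment. After week 1: 2, or 3.

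**Raw count under equal attendance.** If every woman attends the same fraction p of her scheduled visits, the expected ratio is 7p / 23p = 0.30, whatever p is. Counting the 3-month assessment for Momba only gives 8/23 = 0.35; counting it as an extra visit in both arms gives 8/24 = 0.33. The 23 is a ceiling. With N control visits the ratio is 7/N, rising to 7/7 = 1.00 if nothing were required after week 2 (5 + 2 = 7).

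**Simulation.** It used 10 women per arm, 2,000 runs and beta-binomial attendance with within-woman correlation 0.1. True attendance was the same in both arms, at an assumed 60%, 80% or 90%. The test was a Wald test on the log ratio of counts, which approximates the planned random-effects negative binomial model.

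| Schedule (Momba vs control) | Median ratio | Runs declaring a difference |
|---|---|---|
| 7 vs 23, raw count | 0.30-0.31 | 100% |
| 7 vs 23, offset for scheduled visits | 1.00-1.01 | 0.05%-1.65% |
| 23 vs 23, raw count | 0.99-1.00 | 0.05%-4.45% |

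An offset removes the scheduling artefact. So would a common schedule, if In office monitoring applies to both arms.

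**Why an offset on visits is not enough.** Even as a proportion, attendance does not record remote tests. For illustration only, assume the Momba arm had 23 incentive-eligible tests. This borrows the maximum office schedule and relies on the statement that incentive schedules matched. A Momba woman who attends all 7 visits and sends no remote test scores 7/7 = 100% on attendance. She has completed 5/23 = 22% of tests if only week 1 counts, or 7/23 = 30% if weeks 4 and 8 count too. A woman who submits every remote test but misses weeks 4 and 8 scores 5/7 = 71% on attendance, with test compliance of up to 100%.

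**The case against.** The other side has four serious arguments.

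1. **One measure per arm.** The plan's wording joins challenges and office visits with an *or*, which can mean challenges for Momba and visits for controls. If challenges include remote CO tests, this comes close to the remedy below. It supports describing compliance within each arm. It does not supply a common outcome for a model with group and time-by-group effects, and the visit count is still modelled without a denominator.

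2. **The office schedule may cover both arms.** In office monitoring says women, not controls, and ties incentives to the breath test. Visit frequency in weeks 3-12 depended on Sensordrone accuracy, a condition that fits the app arm at least as well. On that reading attendance can be scored in both arms and the 0.30 ratio disappears. This stands: the section conflicts with Intervention Group, and the documents do not settle it. But the stated reason for the paired in-office tests is device validation, and office attendance would still omit the remote tests.

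3. **Two measures are used together.** A reader might infer that a Momba woman who drops the app after week 1 would be judged fully compliant. The documents do not support that. Challenge completion is also assessed and should expose her. The misclassification belongs to the visit-count model alone. A separate analysis also looks at intensity of app use.

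4. **Limited reach.** No threshold is set for compliance, the pilot is declared unpowered, and no abstinence result depends on this measure. That is correct and limits the weight of the point.

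That controls had no challenges is also an inference: from the payment exception in the Control Group section and from the app being issued as intervention equipment. No sentence says so.

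**Conclusion.** The point holds for the between-arm comparison. The plan does not assign its two compliance measures to arms, and neither captures contingency-management compliance in both. If the Intervention Group schedule applies, the visit-count effect reflects schedule and delivery channel: 7 or 8 visits against at most 23, so equal attendance would give a ratio of about 0.30 to 0.35 at the control maximum and closer to 1 with fewer control visits. If In office monitoring applies to both arms, the scheduling artefact goes, but attendance still leaves out the channel through which the app arm mainly receives contingency management.

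It would go too far to say that compliance cannot be shown at all, since it can be described within each arm. It would also go too far to treat the 22%-30% and 71% figures as estimates. They depend on an assumed test count and on combining two sections that conflict.

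**What to change.** - Reconcile Intervention Group with In office monitoring: state which visits each arm was scheduled to make, and for what purpose.
- Define challenges.
- Make the between-arm compliance measure the proportion of each woman's scheduled incentive-eligible CO tests that were submitted, whatever the result: remote or office in Momba, office in control.
- Compare it with a model for proportions, or a count model with an offset for scheduled tests.
- Report challenge completion (Momba only) and training and calibration attendance descriptively, with no group test.

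The cost is analysis-plan wording. Submitted tests should already be on record because incentives followed the breath test, though that is an inference. The denominator must come from the incentive schedule, which these documents do not give. A remote submission and an office visit also demand different effort, and the report should say so.

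### Office-visit compliance is compared between arms as a raw count of visits attended, with no allowance for the number of visits scheduled

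*Combined protocol and SAP*

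**What the plan says.** The Proposed Analytic Plan treats compliance as part of feasibility and says "we will use challenge completion and in-office visit attendance to assess compliance". It continues: "Mixed-effects regression models will be conducted as outlined above for group comparisons". For attendance it names the outcome and the model: "Because number of visits attended is a count variable, random effects regression with a negative binomial model will be used". The only description of the mixed models is under Data Analysis for Pilot RCT: "In each model, we will include fixed effects of time, group (Momba vs. in-office) and time by group, and random subject effects". No section mentions an offset, an exposure term or the number of visits scheduled.

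On what each arm was asked to do:

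- Intervention Group: "The intervention group did most of its CO tests remotely". These women attended on five days of week 1 for training, and then "Intervention group participants came to the office for a visit in Week 4 and Week 8". The other in-person contacts are the baseline, 3-, 6- and 12-month assessments.
- Control Group: "Control group mothers received traditional, in-office contingency management to prevent smoking relapse". It adds: "Financial incentives were delivered according to the same schedule at the same frequency as those delivered to mothers on Momba Live Long". Delivery of the Momba Live Long Intervention gives the length of contingency management as 12 weeks.
- In office monitoring names no arm. It gives five visits in week 1 and two in week 2, then a ceiling of two a week in weeks 3–8 and one a week in weeks 9–12. The actual frequency in weeks 3–12 was tied to how accurate the sensor proved.

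**The concern.** A count of visits attended measures compliance across arms only if both arms were asked to attend equally often. Here remote versus in-office delivery is the contrast under test, so a lighter visit load appears to be built into the app arm. The model as written would score that lighter load as poorer attendance.

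The time terms do not help. A common time effect cannot absorb a schedule that differs by arm within a period. If both arms have five visits in week 1 and the schedules part afterwards, the gap also enters the time-by-group term, where it could be read as app users dropping off. What is at stake is the conclusion on office-visit compliance, which sits beside challenge completion as evidence of feasibility.

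**Working it through.** The plan gives no figure for this analysis, so there is nothing to reproduce. The check counts scheduled visits from the text and works out what the raw-count model would estimate.

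**Scheduled visits, weeks 1–12 (baseline and 3-month assessments left out)**

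- Momba, from Intervention Group: 5 + 1 + 1 = 7. If the two week-2 visits under In office monitoring also apply: 9.
- In office monitoring, maximum: 5 + 2 + (6 × 2) + (4 × 1) = 23.
- Weekly control visits in weeks 3–12 (an assumption, not in the documents): 5 + 2 + 10 = 17.

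**Formula**

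Raw ratio = (Momba scheduled × Momba attendance) / (control scheduled × control attendance) = schedule ratio × attendance ratio.

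**Results**

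| Momba vs control scheduled | Ratio at equal attendance | Ratio at 100% Momba, 50% control |
|---|---|---|
| 7 vs 23 | 7/23 = 0.30 | 7/11.5 = 0.61 |
| 9 vs 23 | 9/23 = 0.39 | 9/11.5 = 0.78 |
| 7 vs 17 | 7/17 = 0.41 | 7/8.5 = 0.82 |
| 9 vs 17 | 9/17 = 0.53 | 9/8.5 = 1.06 |
| equal schedules | 1.00 | 2.00 |

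The true attendance ratio is 1.00 in the middle column and 2.00 in the last. In the first three rows the last column points the wrong way. The equal-attendance ratios are also break-even points: with perfect Momba attendance, the raw ratio stays below 1 unless control attendance falls to 30%, 39%, 41% or 53% or lower, in that order. Adding one 3-month visit to each arm changes little: 8/24 = 0.33, 10/24 = 0.42, 8/18 = 0.44, 10/18 = 0.56.

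**By period, equal attendance**

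- Week 1: 5/5 = 1.00.
- Weeks 3–8: 2/12 = 0.17 at the maximum, or 2/6 = 0.33 with weekly control visits.

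This is the pattern that would surface as a time-by-group effect.

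**Does the small sample hide it?**

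Trials were simulated with 10 women per arm, the size given in the Overview, and 500 replicates per setting. True attendance was equal in both arms at 60%, 80% or 90%. Attendance varied between women as a beta-binomial, and each woman contributed one total, analysed by negative binomial regression with dispersion fixed at 0.05. All of these settings are assumptions.

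| Momba vs control scheduled | Trials with p < 0.05 on the raw count |
|---|---|
| 7 vs 23 | 100% |
| 7 vs 15 (assumed) | 97% to 100% |
| 7 vs 7 | 0% to 1.2% |

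With log(scheduled visits) as offset, the estimated ratio was about 1.00 and the rejection rate 0% to 2.8% in every setting. Rates below 5% arise because the assumed dispersion overstates the variance of a bounded count, which is itself a reason to prefer a binomial form.

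**The case against.** The strongest counter-argument is that the plan may never compare visits with visits. Contingency management reached controls through office visits and app users mostly through remote testing, so challenge completion may be the compliance measure for one arm and attendance for the other. That is a reasonable design, but it is not what is written: the plan calls for group comparisons, specifies a model for the visit count, and nowhere restricts visits to controls.

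The second argument is that unequal schedules are inferred. In office monitoring names no arm, and a ceiling tied to sensor accuracy fits the app arm at least as well as controls. The 23 is a maximum that the text does not assign to controls, and the 17 is assumed. All of this stands, and the ratios must be read as a range that includes 1.00. It does not remove the problem. A shared maximum does not make realised schedules equal, and a frequency that varied in weeks 3–12 is itself a reason to have a denominator.

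The third argument is about weight. This is a pilot that says it is not powered for its outcomes. Compliance has no numerical threshold, whereas participation (60%) and app-arm retention (80%) do. Readers may also see for themselves that remote testing means fewer visits. This limits the consequence, but it does not justify a model that builds the schedule difference into the estimate.

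**Conclusion.** The concern holds. As specified, the between-arm visit comparison mixes how often women were asked to come with how often they came. The direction of distortion suggested by the Intervention Group and Control Group sections is against the app arm. For the schedules considered, the raw ratio under equal attendance runs from 0.30 to 0.53; it is 1.00 only if the realised schedules were the same. These figures rest on the visits listed for the app arm being complete, apart from the week-2 question, and on a control schedule that the documents do not state. Confidence is therefore moderate on size and firm on the missing denominator. The point should be corrected, but its reach is confined to one of the two compliance measures.

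**What to change.** 1. Reconcile the Intervention Group and In office monitoring sections, notably for week 2, and state the office-visit schedule separately for each arm.
2. Take visits attended out of visits scheduled, per woman and period, as the outcome, in a binomial or beta-binomial mixed model. At minimum, keep the negative binomial model and add log(scheduled visits) as an offset.
3. Leave out periods with no scheduled visit, and count assessment visits the same way in both arms.
4. Report challenge completion and remote CO test completion for the app arm separately, each as a proportion of those scheduled.
5. Note in the interpretation that controls were also paid for turning up to scheduled CO visits.

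The cost is a change of SAP wording and one model term or a change of model. The number scheduled for each woman has to be taken from study records, because the frequency in weeks 3–12 was not fixed. If the schedules prove equal, little is lost; if not, the change removes an effect created by the design.
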